8.4.2 Method of Detecting AEs and SAEs

Care will be taken not to introduce bias when detecting AEs and/or SAEs. Open-ended and non-leading verbal questioning of the participant is the preferred method to inquire about AE occurrences.

8.4.3 Follow-up of AEs and SAEs

After the initial AE/SAE report, the investigator is required to proactively follow each participant at subsequent visits/contacts. All AEs/SAEs will be followed until resolution or stabilisation or the participant is lost to follow-up (as defined in Section 7.3). Further information on follow-up procedures is provided in Appendix 10.3.

8.4.4 Regulatory Reporting Requirements for SAEs

- Prompt notification by the investigator to the sponsor of an SAE is essential so that legal obligations and ethical responsibilities towards the safety of participants and the safety of a study intervention under clinical investigation are met.
- The sponsor has a legal responsibility to notify both the local regulatory authority and other regulatory agencies about the safety of a study intervention under clinical investigation. The sponsor will comply with country-specific regulatory requirements relating to safety reporting to the regulatory authority, Institutional Review Boards (IRB)/Independent Ethics Committees (IEC), and investigators.
- An investigator who receives an investigator safety report describing an SAE or other specific safety information (e.g. summary or listing of SAEs) from the sponsor will review and then file it along with the Investigator's Brochure and will notify the IRB/IEC, if appropriate according to local requirements.
- Investigator safety reports must be prepared for suspected unexpected serious adverse reactions (SUSAR) according to local regulatory requirements and sponsor's policy and forwarded to investigators as necessary.

8.4.5 Pregnancy

All participants in this study are male. The investigator must instruct all male participants to inform the investigator immediately should their partner become pregnant.

- Details of all pregnancies in female partners of male participants will be collected from the signing of the ICF and until up to 9 months after the participants last dose of study intervention.
- If a pregnancy is reported, the investigator will record pregnancy information on the appropriate forms (Pregnancy Notification Form– paper form) and submit it to the sponsor within 24 hours of learning of the female partner of male participant becoming pregnant (after obtaining the necessary signed informed consent from the female partner).
- Any pregnancy complication or elective termination of a pregnancy for medical reasons will be reported as an AE or SAE.
- Abnormal pregnancy outcomes (e.g. spontaneous abortion, fetal death, stillbirth, congenital anomalies, ectopic pregnancy) are considered SAEs and will be reported as such.
- The participant's pregnant female partner will be followed to determine the outcome of the pregnancy unless consent is not given/withdrawn. The investigator will collect follow-up information on the participant's pregnant female partner and the neonate and the information will be forwarded to the sponsor.
- Any post-study pregnancy-related SAE considered reasonably related to the study intervention by the investigator will be reported to the sponsor as described in Section 8.4.4. While the investigator is not obligated to actively seek this information in a former study participant's pregnant female partner, he or she may learn of an SAE through spontaneous reporting.

8.4.6 *Disease-Related Events and/or Disease-Related Outcomes Not Qualifying as AEs or SAEs*

Not applicable.

8.4.7 *Adverse Events of Special Interest*

Not applicable.

8.4.8 *Reporting of Study Intervention Errors Including Misuse/Abuse*

- Medication errors are unintentional errors in the prescribing, storing, dispensing, preparing or administration of a study intervention (medicinal product) while under the control of a healthcare professional, participant or consumer.
- Misuse refers to situations where the study intervention is intentionally and inappropriately used not in accordance with the protocol.
- Abuse corresponds to the persistent or sporadic, intentional excessive use of a medicinal product, which is accompanied by harmful physical or psychological effects.
- Study intervention errors and uses outside of what is foreseen in the protocol will be recorded in the eCRF irrespective of whether associated with an AE/SAE or not. It will also be documented in the AE section of the eCRF if associated with an AE. It will be reported in the safety database only if associated with an SAE.

8.5 *Pharmacokinetics*

- Approximately 14 mL of blood will be collected from all participants, and approximately 40 mL of blood from the PK/PD subset participants, for measurement of plasma concentrations of triptorelin 6-month formulation as specified in the SoA (Section 1.3)

- Instructions for the collection, handling and shipment of biological samples will be provided by the sponsor and described in the study laboratory manual. The accurate date and time (24-hour clock time) of each sample collection must be recorded.
- Plasma samples will be used to evaluate the PK of triptorelin 6-month formulation. Each plasma sample will be divided into two aliquots (one primary and one backup). Samples collected for analyses of triptorelin concentration may also be used to evaluate safety or efficacy aspects related to concerns arising during or after the study.
- During the study, the nominal sample collection times may be changed, but the total number of samples will not increase. The exact dates and times of blood sample collection and study drug administration must be recorded in the eCRF.
- On predetermined dates, plasma samples will be shipped to the bioanalytical service provider under frozen conditions. For security reasons, the back-up aliquots will not be shipped until the primary aliquots have arrived. Upon receipt at the bioanalytical service provider, samples will be checked and stored until analysis.
- Plasma will be analysed to determine concentrations of triptorelin using a validated, specific and sensitive LC-MS/MS methods.
- Surplus plasma samples will be used in China and will not be shipped outside China. Surplus plasma samples will be managed anonymously and will not be identifiable.
- Residual plasma samples remaining from the analyses may also be retained by the sponsor for up to 5 years after completion of the study. This could include using leftover plasma for long-term stability or reproducibility assessments.

9 STATISTICAL CONSIDERATIONS

9.1 Statistical Hypotheses

No statistical hypotheses are planned for this study.

9.2 Sample Size Determination

The sample size was estimated based on data from the previous Study DEB-TRI6M-301, 97.5% of participants achieving castration and 93% of participants maintaining castration from Week 8 to Week 24.

Sample size is calculated to fulfil the co-primary efficacy criteria of this study, which is to assess the proportion of participants achieving castrate levels of testosterone on Day 29 and the proportion of participants maintaining the castrate levels of serum testosterone from Week 8 to end of Week 24. A total of 195 participants with advanced prostate cancer will be enrolled to receive the triptorelin pamoate 22.5 mg 6-month formulation.

For an exact binomial test of a proportion with a two-sided nominal significance level of 0.05 and null proportion of 85%, a sample size of 165 participants has an exact power of 88.3% when the true proportion is 93% (of participants maintaining castration from Week 8 to Week 24). This sample size of 165 participants has a power >99.9% when the true proportion is 97.5% (of participants achieving castrate testosterone levels). Exact two-sided 95% confidence interval (CI) for a binomial proportion was computed by SAS using the exact binomial distributions.

Assuming the dropout rate will be around 15%, a sample size of 195 participants in total is planned for this study.

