9.4.1.2 Significance Testing and Estimations

As this is a descriptive safety and efficacy study, no formal statistical testing will be carried out.

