2.3 Sample Size Determination and Power

The sample size was estimated based on data from the previous Study DEB-TRI6M-301, 97.5% of participants achieving castration and 93% of participants maintaining castration from Week 8 to Week 24.

Sample size is calculated to fulfil the co-primary efficacy criteria of this study, which is to assess the proportion of participants achieving castrate levels of testosterone on Day 29 and the proportion of participants maintaining the castrate levels of serum testosterone from Week 8 to end of Week 24. A total of 195 participants with advanced prostate cancer will be enrolled to receive the triptorelin pamoate 22.5 mg 6-month formulation.

For an exact binomial test of a proportion with a two-sided nominal significance level of 0.05 and null proportion of 85%, a sample size of 165 participants has an exact power of 88.3% when the true proportion is 93% (of participants maintaining castration from Week 8 to Week 24). This sample size of 165 participants has a power >99.9% when the true proportion is 97.5% (of participants achieving castrate testosterone levels). Exact two-sided 95% confidence interval (CI) for a binomial proportion was computed by Statistical Analysis System (SAS) using the exact binomial distributions.

Assuming the dropout rate will be around 15%, a sample size of 195 participants in total is planned for this study.

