5.7.1.1 Significance Testing and Estimations

The statistical analysis of efficacy and safety is only descriptive therefore no formal statistical significance testing will be performed.

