5.7.1.3 Statistical/analytical issues

Adjustments for Covariates

This is a single-arm study, and no statistical comparisons will be performed, so covariates adjustment is not required.

Interim Analyses and Data Monitoring

Please refer to section 3.

Multicentre Studies

This is a multicentre study conducted in China.

Multiple Comparisons/Multiplicity

No multiple testing will be performed in this study because this is a single-arm descriptive safety and efficacy study.

Active-Control Studies Intended to Show Equivalence (if applicable)

Not applicable.

5.7.2 *Analysis of Primary Efficacy Endpoint*

5.7.2.1 *Endpoint, Treatment Effect and Estimand Definition*

The co-primary endpoints of efficacy are

- To determine the percentage of participants achieving castrate levels of serum testosterone (<50 ng/dL or 1.735 nmol/L) on Day 29 ± 3 days (Week 4) and
- To determine the percentage of participants maintaining the castrate levels of serum testosterone (<50 ng/dL or 1.735 nmol/L) from Week 8 (Day 57 ± 3 days) to Week 24 (Day 169 ± 3 days).

Percentage of participants achieving castrate levels of serum testosterone on Day 29

The percentage of participants achieving castrate levels of serum testosterone on Day 29 will be obtained as the number of participants achieving castrate levels on Day 29, divided by the number of participants in the FAS. The formula is

$$\text{Percentage} = \frac{\text{Number of participants achieving castrate levels on Day 29}}{\text{Number of participants in the analysis set}} \times 100$$

Percentage of participants maintaining castrate levels from Week 8 to Week 24

Percentage of participants maintaining castrate levels of serum testosterone from Week 8 to Week 24 for the FAS will be calculated as the number of participants achieving castrate levels of serum testosterone at all visits from Week 8 to Week 24, divided by the number of assessable participants in the analysis set. The formula is

$$\text{Percentage} = \frac{\text{Number of participants maintaining castrate levels from Week 8 to Week 24}}{\text{Number of assessable participants in the analysis set}} \times 100$$

To derive the percentage of participants maintaining castration levels of testosterone, missing data between Week 8 and Week 24 will be handled as follows:

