- (a) In participants escaping castration at a certain visit (The escape event is defined as participant with a testosterone level >50 ng/dL), subsequent missing data is irrelevant; that is to say, participant will be treated as failure in that case.
- (b) Participants maintaining castration up to a certain visit with missing data afterwards (drop-out due to non-drug-related reasons) will be excluded from the analysis.
- (c) Participants maintaining castration up to a certain visit with missing data afterwards (drop-out due to drug-related reason) will be treated as having escaped castration (failure). Drug-related reason for drop-out is drug-related adverse event or death.
- (d) Missing data at 1 or more visit(s) between two visits where castration levels are maintained will be handled as missing for that particular visit, and the participant will be considered to have maintained castration if all visits with available results are maintained.

To derive the percentage of participants maintaining castrate levels of testosterone, assessable participants are defined as the number of participants having values at all visits and all participants having missing data according to the criteria a), c) and d) mentioned above. Participants having missing data according to the criteria b) will be excluded from this calculation. Participants who discontinue before Week 8 will also be excluded from this calculation.

Because this is a descriptive post-approval commitment study, and the protocol was approved before National Medical Products Administration (NMPA) implementation of ICH E9 (R1), estimands will not be considered for this study.

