5.7.2.2 Primary Analysis

The two primary endpoints will be tabulated with two-sided 95% CIs separately using the Clopper Pearson exact method for the FAS.

Castrate levels of serum testosterone will be summarized with descriptive statistics. Value below the lower limit of quantification (LLOQ) will be substituted by the LLOQ value for summary. Whether castrate level of serum testosterone is achieved (Yes/No) will also be summarized by visit.

Individual testosterone level data versus visit will be plotted by participant on a semi-logarithmic scale on the FAS with a dash line to indicate the testosterone limit of castration (50 ng/dL or 1.735 nmol/L) and a second dash line for the LLOQ. The arithmetic mean (\pm SD) and median testosterone levels versus visit will also be presented.

A testosterone level will be listed on all participants enrolled by participant and visit. All values below the limit of quantification will be listed as such.

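### Is it a defect that 165 participants are justified by the power of an exact test against 85% that the plan does not run?

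*Protocol*

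**What the plan says.** Protocol 9.2, with matching text in the Synopsis and SAP 2.3, sizes the study by a power calculation: "For an exact binomial test of a proportion with a two-sided nominal significance level of 0.05 and null proportion of 85" per cent. SAP 2.3 gives the result as "null proportion of 85%, a sample size of 165 participants has an exact power of 88.3% when the true proportion is 93" per cent, and adds power above 99.9% at a true 97.5% for Day 29. Allowing for about 15% dropout gives 195 enrolled. The next sentence in each place mentions an exact two-sided 95% interval but attaches no threshold to it.

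Elsewhere the plan is descriptive:

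- Protocol 9.1: "No statistical hypotheses are planned for this study"; SAP 2.1 agrees.
- Protocol 9.4.1.2: "no formal statistical testing will be carried out".
- SAP 5.7.1.1: "no formal statistical significance testing will be performed".
- SAP 5.7.1.3: "No multiple testing will be performed in this study because this is a single-arm descriptive safety and efficacy study".
- SAP 5.7.2.1, explaining why estimands are not used: "Because this is a descriptive post-approval commitment study".
- SAP 5.7.2.2: "The two primary endpoints will be tabulated with two-sided 95% CIs separately using the Clopper Pearson exact method for the FAS".

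The sample-size text labels the 93% planning rate as Week 8 to Week 24 and attributes it to Study DEB-TRI6M-301. The Synopsis rationale and Protocol 2.2 report 93.0% (107/115) from the earlier phase III study for Week 8 to the end of Week 48.

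**The concern.** A power figure is the probability of a defined event, here rejecting 85%. If the plan never evaluates that event, the reader cannot tell what the 88.3% promises, what result would count as meeting the co-primary criteria, or whether both endpoints must meet them. The study is open-label and single-arm, and the protocol's rationale ties it to registration in China, so the results will be interpreted. A benchmark used for sizing but absent from the analysis could be invoked or passed over once the data are known, and near the boundary one participant decides which side of 85% the lower limit falls on.

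The 93% is also the input that drives the power. If it belongs to a different window, the 88.3% might seem to rest on the wrong rate.

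**Working it through.** **Inputs.** From Protocol 9.2 and SAP 2.3: n = 165; null proportion 0.85; two-sided 0.05, so 0.025 per tail; true proportions 0.93 and 0.975; dropout 15%; 195 enrolled. From Protocol 2.2: 117/120 and 107/115.

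**1. Reproduce the plan's power.** The critical count c is the smallest value with P(X ≥ c | 165, 0.85) ≤ 0.025.

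- P(X ≥ 149) = 0.0309, too large.
- P(X ≥ 150) = 0.0173, so c = 150 (150/165 = 90.9%).
- P(X ≥ 150 | 165, 0.93) = 0.8832, the stated 88.3%.
- P(X ≥ 150 | 165, 0.975) = 0.999995, the stated >99.9%.
- The lower rejection region (130 or fewer) adds nothing material.
- 165 / (1 − 0.15) = 194.1, rounded up to 195.

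**2. Compare with the planned interval.** The Clopper-Pearson lower limit for x responders is the 0.025 quantile of Beta(x, n − x + 1).

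| Responders of 165 | Observed | 95% interval |
|---|---|---|
| 149 | 90.3% | 84.7% to 94.4% |
| 150 | 90.9% | 85.4% to 94.8% |
| 153 | 92.7% | 87.6% to 96.2% |
| 161 | 97.6% | 93.9% to 99.3% |

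The lower limit first passes 85% at 150, the critical count in step 1. This is no coincidence: the Clopper-Pearson interval is the inversion of the exact test. The powered event and the event that the planned lower limit exceeds 85% are therefore the same, with probability 88.3% at a true 93%.

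**3. Both endpoints together.** If both were read against 85%, the joint probability would lie between 0.8832 + 0.999995 − 1 = 0.8832 and min(0.8832, 0.999995) = 0.8832. It is 88.3% whatever their correlation, so the missing both-or-either rule makes no difference to the sizing.

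**4. Dependence on the denominator.** SAP 5.7.2.1 divides by the whole analysis set for Day 29 and by assessable participants for maintenance, so neither denominator need be 165.

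| n | Smallest count with lower limit above 85% | Power at 93% |
|---|---|---|
| 160 | 145 | 90.4% |
| 165 | 150 | 88.3% |
| 170 | 154 | 91.2% |

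**5. The window of the 93%.** 107/115 = 93.04% and 117/120 = 97.5%, which match the planning rates; that the two descriptions concern one study is inferred from this. A man castrate at every visit from Week 8 to 48 is also castrate at every visit from Week 8 to 24. With the same denominator and missing-data rules (an assumption), the Week 8 to 24 rate is at least 93%. Power with 165 rises with the true rate: 75.3% at 92%, 88.3% at 93%, 96.0% at 94%, 99.1% at 95%. The probable error is on the safe side.

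**The case for a change.** The strongest case for a change is that 88.3% is the probability of something the plan does not undertake to look at. The co-primary criteria in Protocol 9.2 amount to estimating two proportions, and the interval sentence beside the power statement sets no threshold. Fixing the reading in advance would cost no participants and no power, and would protect the sponsor's own conclusion. On the text this is right: the interpretive sentence is absent, and the two windows for 93% do not agree.

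The consequence is weaker than it sounds. The 85% is on record in three places, so any reader can set the reported lower limit beside it, and the sponsor cannot easily substitute another figure. SAP section 1 requires unplanned analyses to be identified as such in the study report. Testosterone is measured centrally by LC-MS/MS, which limits what open-label knowledge can do to the endpoint. That one participant decides is true of every binomial cut-off.

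The remedies also have costs. A success criterion would reverse the descriptive status the plan declares repeatedly. It would have to be carried through the Synopsis, Protocol 9.1, 9.4.1.2 and 9.4.2, and SAP 2.1, 5.7.1.1, 5.7.1.3, 5.7.2.1 and 5.7.2.2, and the protocol amendment would need ethics approval. Replacing the power statement with a precision argument would leave the same number, the same intervals and no benchmark.

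**Conclusion.** No change to the plan is needed. The sample-size arithmetic is correct, and the planned Clopper-Pearson interval carries the same information as the test used for sizing. Followed as written, the plan gives sound estimates and intervals, and neither they nor the 195 enrolled would alter if 85% were named in the analysis sections. Using a test to choose n and then reporting an interval is a fair way to size a descriptive study. A reader who wants the comparison can make it from the reported table.

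What remains is missing detail and a clerical slip. The detail is whether 85% is a reference value or a sizing device only. The slip is the window of the 93%, which changes neither the number enrolled nor the power at 93%.

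This rests on three things: the study remains descriptive, as both documents say; the 150/165 threshold is illustrative, because the actual denominators may differ; and the view that 88.3% is conservative assumes that both passages describe the same earlier study with matching denominators and missing-data rules. The documents do not give that study's Week 8 to 24 rate.

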9.3 Analysis Sets

For the purposes of analysis, the following analysis sets are defined:

Participant Analysis Set	Description
Screened	All participants screened (i.e. who signed the informed consent).
Safety Set	The safety set will contain all participants who receive the single dose of study intervention.
Full Analysis Set	The FAS will contain all treated participants who complete the study or is a treatment failure. Completing the study is defined as having serum testosterone measurement at baseline, Day 29 and Day 169. Treatment failure is defined as escaping castration (testosterone level ≥ 50 ng/dL) at any assessments on and after Day 29 during the study, or premature discontinuation from the intervention period due to drug-related reasons (adverse event or death).
Per Protocol Set	All participants in the FAS who have no impacting major protocol deviations (i.e. that could potentially affect the primary efficacy endpoint outcome for the participant) as described in the protocol deviations document.
Rich PK Analysis set (for non-compartmental analysis)	Participants in the PK/PD subset who receive one dose of study intervention, have no major protocol deviations affecting the PK variables, and who have a sufficient number of plasma concentrations to estimate the main PK parameters (maximum observed plasma drug concentration (C_{max}), time to maximum observed drug concentration (t_{max}) and area under the plasma concentration time curve (AUC))
Population PK Analysis Set	All participants who received one dose of triptorelin and who have at least one triptorelin plasma concentration and no major protocol deviations affecting PK variables.

Participant Analysis Set	Description
Rich PD Analysis Set	all participants in the PK/PD subset who have a sufficient number of PD (testosterone) measurements to estimate the main PD parameters (maximum observed concentration (C_{max}), time to maximum observed concentration (t_{max}) and time to castration (t_{castr}))

FAS=full analysis set; PD=pharmacodynamic PK=pharmacokinetic

The efficacy analysis for the primary and secondary efficacy endpoints will be presented for the full analysis set (FAS) and per protocol (PP) population. The analysis of the safety data will be performed based on the safety set and analysis of PK and PD in the relevant PK analysis set

